Significant contributions of the proposed research: The proposed study will be one of the first large, longer-term RCTs testing low-cost behavioral nudges among a very low-income group of consumers. This study will improve upon prior work in several ways. First, we will use a randomized-controlled design to follow a large cohort of clients over one year. Second, we will analyze objective transaction data of all food selections made at the pantry over four months (one month pre-baseline and three months post-baseline) at the individual-level and link that with food intake and health data. Third, we will measure fruit and vegetable intake with an objective biomarker and questionnaire, and we will objectively assess health outcomes including weight and blood pressure. This will also be the first study to evaluate these behavioral techniques in the context of an innovative online ordering platform that has the potential to be the future gold standard for food pantries. Although web-based ordering systems are not yet widespread in food pantry settings, their use is growing rapidly. Two of the largest food pantries in New York City (NY Common Pantry and St. John's Bread and Life) have both implemented an online ordering system and the St

Johns system has been replicated in Nevada. Our food pantry partner has also replicated their online system in a neighboring county and the pantry has hosted site visits and shared best practices with the Metropolitan Council on Jewish Poverty who has 30 distribution sites and is moving toward an online system. This work also makes a significant contribution because very few studies of behavioral nudges have been conducted among populations with very high concentrations of poverty. Finally, our research team represents an interdisciplinary collaboration that includes academic and community partners. This partnership enables us to gain valuable insights from practitioners and ensures the research questions we are asking are relevant to practice as well as scientific discovery. This partnership will also help us disseminate these results through conventional academic channels as well as to practitioners. Given widespread interest in implementing these types of low-cost nudges to improve food choices, such rigorous evaluations are sorely needed.

1. Mozaffarian D. Dietary and policy priorities for cardiovascular disease, diabetes, and obesity: a comprehensive review. *Circulation*. 2016;133(2):187-225.

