

Study Design

Design

We will use a random number generator to assign study participants to one of 2 conditions: 1) usual care (control); or 2) behavioral economic intervention. The research team will create the randomization list and a research assistant will assign the participant to the correct online platform condition, but the investigators and data analysts will remain blind to group assignment. This study will contain two parallel groups. Although participants will not initially be aware of the other study condition, they will not be blinded to study condition because those in the intervention condition will be viewing the altered ordering platform as they shop.

Study duration

This study is estimated to take four years. Year 1 will be spent finalizing the research protocol, updating the food pantry web-platform, categorizing pantry food with traffic lights, and hiring and training study staff. We will begin recruiting participants and collecting data in the second half of year 1. Subjects' participation will be for four months (one month pre-baseline, three months post-baseline). Participant recruitment will continue through years 2 and 3 of the study and data collection will continue through years 2, 3 and the first half of year 4. Year 4 will be spent cleaning and analyzing data and preparing manuscripts.

Characteristics of the Study Population

Target population

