Ukrainian translation was not done because we learned from the food pantry staff and our conversations with clients that the clients are largely English or Russian speaking and do not need Ukrainian language materials. Furthermore, the online ordering system at the food pantry is only available in English or Russian, so all clients shopping there must be able to communicate in one of those two languages. Finally, no clients to date have requested Ukrainian materials.

Attachments:

[fp_PostCards Recruitment_EN_v1.0_2020-12-14.pdf](#) (English post card)

[fp_PostCards Recruitment_RU_v1.0_2020-12-14.pdf](#) (Russian post card)

[fp_Translation for UPenn_RU_2020-12-14.pdf](#) (Certified Translation of PostCards Recruitment 2020-10-06_EN.pdf)

[fp_Poster_EN_v1.0_2020-12-14.pdf](#) (English poster, Certified Russian Translation to be included in subsequent modification)

Will the recruitment plan propose to use any Penn media services (communications, marketing, etc.) for outreach via social media avenues (examples include: Facebook, Twitter, blogging, texting, etc.) or does the study team plan to directly use social media to recruit for the research?

No

The following documents are currently attached to this item:

There are no documents attached for this item.

Subject compensation*

Will subjects be financially compensated for their participation?

Yes

The following documents are currently attached to this item:

There are no documents attached for this item.

If there is subject compensation, provide the schedule for compensation per study visit or session and total amount for entire participation, either as text or separate document

Prior to the COVID-19 pandemic, the study was conducted with three assessment points at baseline, 3-months, and 12-months. Since the pandemic, we have changed study protocols to only conduct assessments at baseline and 3-months. Participants who were enrolled prior to the pandemic who have not reached the 12-month time point have been notified that there will be no data collection at 12 months. For completing the assessments at baseline and 3-months, we will compensate participants \$25 for each visit. This incentive will be broken up into the following payments: \$10 for surveys, \$5 for blood pressure measurement, \$5 for weight measurement, and \$5 for veggie meter

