(diet quality) measurement. We will also remunerate participants \$25 for completing a training on how to use the pantry online ordering system. Participants will be paid via ClinCards. These are debit cards that we have successfully used in other longitudinal research studies that enable us to automatically load money onto a participants' card, which they can then use at any store like a debit card. We will also approve Check payments for participants who are unable to receive ClinCards. To strengthen cohort retention, we will incentivize successful online shopping each of the three months that participants are in the study after baseline measurements. For completing their baseline order, participants will receive a \$5 payment, for months 1 and 2, participants will receive \$3, and for month 3, participants will receive \$4, totaling \$15 for all orders. The total financial compensation for participation is \$90 (\$25 + \$25 + \$25 + \$15).

Prior to the COVID-19 pandemic, we planned to strengthen cohort retention during the study by entering each participant into several lotteries where 10 people had the chance of winning \$5 prizes and one person would win a \$100 prize. Because of the shortened timeline of the study (1 year to 3-months), we will no longer use a lottery to encourage cohort retention. We also planned to provide a \$3 incentive twice for participants confirming their contact information at 3-months and 12-months. Because of the shortened study timeline and that we will now incentivize shopping monthly, we will no longer provide a \$3 incentive for confirming contact information.

Study Procedures

Suicidal Ideation and Behavior

Does this research qualify as a clinical investigation that will utilize a test article (ie- drug or biological) which may carry a potential for central nervous system (CNS) effect(s)?

No

Procedures

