As part of the informed consent process, participants will be asked whether they would like to be contacted about future opportunities to participate in other research studies. Their response will be documented on the informed consent form (either on REDCap or a paper form). If they answer affirmatively, their name, e-mail, and phone number will be added to a REDCap database separate from this project and will be used for recruitment for studies within the PEACH Lab at the University of Pennsylvania. This database will not be shared with anyone outside of the Lab.

After consenting to participate, we will collect basic contact and demographic data consisting of the following elements: name, date of birth, address, phone number, email address, language, race, ethnicity, education level, gender, children living in household, and cigarette smoking behavior.

We will conduct study assessments with participants at two time points: baseline and 3-months post intervention. We will conduct baseline measurements of height, weight, blood pressure, and diet quality using the Veggie Meter with participants at their homes or at the food pantry following all current COVID-19 safety guidelines. We will use a script to describe measurements when calling participants to schedule their measurement appointments (fp_Script to describe measurements to participants). To aid with contactless measurements, we will provide participants with printed instructions (fp_Measurement Instructions for Participant, fp_Veggie Meter Instructions for Participant).

These documents have been professionally translated

We will administer diet and health surveys (fp_DietSurvey, fp_HealthSurvey) electronically through REDCap surveys. We will provide the option of doing surveys over the phone on an as-needed basis for participants not comfortable with electronic surveys.

Participants will receive \$25 for completing all components of baseline measurements (\$10 for surveys, \$5 for blood pressure, \$5 for weight, and \$5 for veggie meter). We will provide participants with their blood pressure and weight results at the time of measurement using printed cards (fp_Results Cards). We will provide weight and blood pressure results only and not BMI or Veggie Meter results as these are not meaningful results for participants. Blood pressure results include a desirable range from low to high blood pressure, and direct participants to consult with their doctor if results are outside this range.(1)

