Are you conducting research outside of the United States?

No

Analysis Plan

Data will be descriptively summarized and evaluated for quality prior to the evaluation of primary and secondary endpoints. Means and standard deviations will be used to characterize continuous variables such as weight and blood pressure, and frequencies and percentages will be used to describe categorical variables such as nutritional quality. Medians and interquartile ranges will be reported for continuous variables that exhibit skewness. Data will be descriptively summarized overall and by condition. All outcomes will be analyzed at the customer level except for nutritional quality, which will be analyzed at the item level. Analyses will employ population-averaged marginal models estimated by Generalized Estimating Equations (GEE) to account for correlations among longitudinal monthly measurements and items purchased per food pantry customer. Marginal models estimated by GEE are advantageous for their population-level interpretation and robustness of estimated effects to the assumed correlation structure among repeated measurements (meaning unbiased estimates of the effect of the behavioral economic intervention will be obtained whether or not the correlation among repeated measurements within a food pantry customer is modeled correctly). Clusters will be defined at the level of the customer for all analyses, and independence working correlation will be assumed. Linear models will be used for continuous outcomes and logistic models for ordinal outcomes such as nutritional quality. Models will include 2-level intervention, month, and the interaction of intervention and month as categorical variables. The primary analysis of testing the effectiveness of the behavioral economic arm compared to the control arm will be evaluated by the joint test of the null hypothesis test that intervention-month interaction coefficients are 0, denoting no difference in the change in respective outcomes from baseline to month 3 between intervention groups. Secondary analyses will test for changes in intervention effects over time by testing whether intervention-month interaction coefficients are equivalent at month 3. We will evaluate the sensitivity of estimated intervention effects to imbalances in baseline covariates and missing data. To assess the impact of imbalance in baseline covariates, outcomes will be reanalyzed in models that adjust for baseline covariates that differ significantly at the 0.05 level by intervention arm. We will evaluate sensitivity to missing data by inverse probability of weighted GEE and multiple imputation. The Holm procedure⁷⁷ at a family-wise error rate of 0.05 will be used to account for multiple comparisons in testing differences in five primary outcomes between the two groups (nutritional quality of food selected, fruit and vegetable intake based on the food frequency questionnaire, weight, and blood pressure). Similar analyses of dermal carotenoids will be performed as secondary endpoint analyses.

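### The secondary test of change in effect over time cannot be run as specified: two arms give one coefficient at month 3, and only food orders have more than one follow-up

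*Combined protocol and SAP*

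**What the plan says.** The Design section has two parallel arms; a random number generator will "assign study participants to one of 2 conditions: 1) usual care (control); or 2) behavioral economic intervention". The Analysis Plan fits marginal models by GEE and specifies: "Models will include 2-level intervention, month, and the interaction of intervention and month as categorical variables". The primary analysis is a "joint test of the null hypothesis test that intervention-month interaction coefficients are 0", read as no difference between arms in change from baseline to month 3. The next sentence gives the secondary analysis: "Secondary analyses will test for changes in intervention effects over time by testing whether intervention-month interaction coefficients are equivalent at month 3". It names no outcome.

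On timing, the Subject compensation section states: "Since the pandemic, we have changed study protocols to only conduct assessments at baseline and 3-months". The Procedures section agrees: "We will conduct study assessments with participants at two time points: baseline and 3-months post intervention". It lists weight, blood pressure, the Veggie Meter and the diet survey as the measurements repeated at 3 months. Food transactions are different. The Background describes analysing them "over four months (one month pre-baseline and three months post-baseline) at the individual-level", and under Subject compensation "we will incentivize successful online shopping each of the three months that participants are in the study after baseline measurements".

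**The concern.** A test of whether an intervention effect changes over time compares the effect at one follow-up with the effect at another. The sentence instead asks whether several coefficients agree at one month. With a two-level intervention there is only one coefficient at that month.

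Most outcomes also have a single follow-up, so no second effect estimate exists for comparison. The pre-pandemic schedule (3 and 12 months) had two follow-ups; the current one does not.

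At stake is whether the trial can say anything pre-specified about an effect growing or fading. For most outcomes it cannot. For food orders it could, but the analyst would have to choose the contrast, possibly after seeing the data. The nearest test that runs on the sentence as written is the month-3 coefficient against 0. For two-visit outcomes that repeats the primary test and says nothing about time.

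**Working it through.** The plan gives no figure for this test, so there is none to reproduce. The check is a count of coefficients under the plan's own model.

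**Inputs**
- Arms: A = 2 (Design).
- Model: intervention, categorical month and their interaction (Analysis Plan).
- Time points for weight, blood pressure, questionnaire and dermal carotenoids: baseline and month 3, so T = 2 (Subject compensation; Procedures).
- Time points for food orders: one pre-intervention month plus months 1, 2 and 3, so T = 4 (Background; Subject compensation). This treats the baseline order as unexposed.

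**Model.** Take baseline as the reference month, and let δₘ be the interaction coefficient at month m:

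link(mean) = β₀ + β₁·arm + Σ γₘ·[month = m] + Σ δₘ·arm·[month = m]

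**Formulas**
- Interaction coefficients in total: (A − 1)(T − 1).
- Interaction coefficients at any one month: A − 1 = 2 − 1 = 1.
- Primary joint test, all δₘ = 0, with A = 2: T − 1 df.
- Change in effect over time, all δₘ equal, with A = 2: T − 2 df.

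**Results.** The rank of the constructed design matrix equals 2T in each row, so every coefficient counted is estimable.

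| Layout (months) | Rank | Interaction coefficients | At month 3 | Primary joint test | Equality over time |
|---|---|---|---|---|---|
| 0, 3 (weight, blood pressure, questionnaire, carotenoids) | 4 | 1 | 1 | 1 df | 0 df |
| 0, 1, 2, 3 (food orders) | 8 | 3 | 1 | 3 df | 2 df |
| 0, 3, 12 (pre-pandemic assessments) | 6 | 2 | 1 | 2 df | 1 df |

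**Reading the table**
1. The month-3 count is 1 in every row. Equality of coefficients at month 3 is therefore not a contrast for any outcome, and would not have been one under the pre-pandemic schedule with two arms.
2. For two-visit outcomes the only coefficient is δ₃. The primary test is δ₃ = 0, and no second coefficient is left to compare with it.
3. For food orders the proper null hypothesis is δ₁ = δ₂ = δ₃, which is two independent contrasts (δ₁ − δ₂ = 0 and δ₁ − δ₃ = 0), hence 2 df. With equally spaced months, the linear trend reduces to δ₃ − δ₁ = 0, which has 1 df.

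**Sensitivity to the baseline-order assumption.** If the pre-baseline month and the baseline order are modelled as separate levels (T = 5), there are 4 interaction coefficients. Equality of all four has 5 − 2 = 3 df; equality across months 1 to 3 alone still has 2 df.

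**The case against.** The strongest reply is that the sentence is loosely worded rather than empty. It names no outcome, uses the plural for coefficients, and sits in a section that refers to monthly measurements. A sympathetic reader could take it to mean equality of the monthly coefficients up to month 3, for the one outcome with monthly data. Those coefficients are already in the primary model for food orders, so the time pattern will be estimated anyway and only a formal test is missing. It is a secondary analysis, and primary inference does not depend on it.

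Part of this stands. A valid test does exist for food orders, the practical loss is limited, and the primary tests are untouched. How an analyst would handle the sentence is also a prediction that the documents cannot settle. The sympathetic reading does not repair the text, however. The models are described for the outcomes generally, with nothing confining this analysis to food orders. The wording also fits several different null hypotheses: equality across months 1 to 3, month 3 against an earlier month, a linear trend, or month 3 against 0.

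Two further points were raised. Some early participants may have reached 12 months before that visit was dropped. Their number is not given, and the Analysis Plan, which runs from baseline to month 3, gives such data no role. It is also not stated whether the baseline order is placed on the altered platform. That affects the degrees of freedom only if the baseline order is counted as a further follow-up.

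**Conclusion.** The concern holds. The secondary test is wrong as written: its contrast is undefined for every outcome, because two arms leave one interaction coefficient at month 3. For weight, blood pressure, questionnaire intake and dermal carotenoids the current schedule leaves 0 df for any change-over-time test, however it is worded. For nutritional quality of food orders the aim can be met with 2 df, or with a 1-df trend, but the plan does not specify that test.

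The 0 df rests on the current two-visit schedule and a baseline-to-month-3 analysis. The 2 df assumes one pre-intervention and three post-baseline months, with a single interaction coefficient per post-baseline month. The documents do not say how the sentence came to be worded this way, and the finding does not depend on it. The correction should be made, but it bears on a secondary analysis only.

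**What to change.** Replace the sentence in the Analysis Plan with one that does three things:

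- Limit the over-time analysis to nutritional quality of food orders.
- Name one contrast before the data are seen: either equality of the month-1, month-2 and month-3 intervention-by-month coefficients (2 df) or a linear trend across them (1 df).
- State that no over-time analysis will be made for weight, blood pressure, questionnaire intake or dermal carotenoids, because each has a single follow-up.

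The same edit should say which order is the reference month and whether the baseline order is placed before or after exposure to the altered platform, so that the degrees of freedom are fixed.

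The cost is a short text change. No new data are needed, since monthly transactions are already captured, and the primary tests, the Holm procedure and the sample size stay as they are.

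### The baseline-imbalance sensitivity analysis chooses covariates by a p<0.05 balance test and leaves their form of entry open, so it may adjust for nothing or, for linear outcomes with complete visits, change nothing

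*Combined protocol and SAP*

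**What the plan says.** The Analysis Plan has one sentence on baseline adjustment. It says that "outcomes will be reanalyzed in models that adjust for baseline covariates that differ significantly at the 0.05 level by intervention arm". It gives no list of candidate covariates, no balance test, no form of entry and no rule for the case where nothing differs.

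The model being adjusted is described just before: "Models will include 2-level intervention, month, and the interaction of intervention and month as categorical variables". Clusters are customers and "independence working correlation will be assumed". The primary test is on the intervention-by-month coefficients. On link functions: "Linear models will be used for continuous outcomes and logistic models for ordinal outcomes such as nutritional quality".

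Under Study Procedures (Procedures), the contact and demographic items collected are "name, date of birth, address, phone number, email address, language, race, ethnicity, education level, gender, children living in household, and cigarette smoking behavior". On physical measures: "We will conduct baseline measurements of height, weight, blood pressure, and diet quality using the Veggie Meter". A diet survey and a health survey are also given at baseline. On timing: "We will conduct study assessments with participants at two time points: baseline and 3-months post intervention".

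**The concern.** There are two separate weaknesses.

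**Selection.** Arms are assigned by a random number generator (Study Design, Design), so any baseline difference is due to chance. A test at 0.05 flags a strong predictor of change and an irrelevant covariate equally often, 5% of the time each. The reanalysis can end up with no covariates, or can leave out a prognostic one that narrowly misses the cut-off.

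**Form of entry.** The parameter tested is a difference in change. A covariate that is constant over time and entered only as a main effect has no route to that parameter in a linear model with complete visits.

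The unadjusted change-from-baseline contrast already removes time-constant covariate effects for linear outcomes. What can remain is imbalance in covariates related to change, and a main-effect adjustment cannot detect that. A report that questionnaire intake, weight or blood pressure results are robust to imbalance would then be true by construction among participants with complete visits.

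**Working it through.** The plan states no figure on this point, so there is none to reproduce.

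**1. Chance that nothing is flagged.** The demographic list gives 8 usable covariates: age (from date of birth), language, race, ethnicity, education, gender, children in household, smoking. Height, weight, systolic and diastolic pressure, carotenoid score and questionnaire intake make 14. These counts are inferred; the plan sets no list. With k independent candidates, P(none) = 0.95^k, and correlation among candidates raises it:

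| k | P(none flagged) |
|---|---|
| 8 | 0.95^8 = 0.663 |
| 14 | 0.95^14 = 0.488 |
| 20 | 0.95^20 = 0.358 |

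With the target of 500 split 250 per arm (assumed), a covariate is ignored if its standardised difference is below 1.96 × √(2/250) = 0.175, however prognostic it is.

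**2. What an imbalance does to the unadjusted result.** Let z be the covariate's balance statistic and R its correlation with change. The estimate shifts by R·z SE, and the conditional type I error is P(|N(Rz, 1−R²)| > 1.96).

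| R | z = 1.9 (just missed): shift, error | z = 2.5 (flagged): shift, error |
|---|---|---|
| 0.1 | 0.19 SE, 5.3% | 0.25 SE, 5.6% |
| 0.2 | 0.38 SE, 6.2% | 0.50 SE, 7.4% |
| 0.3 | 0.57 SE, 7.7% | 0.75 SE, 10.5% |

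The documents give no values for R or z; all are assumed.

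**3. Why a main effect changes nothing in the linear case.** Add γx to the model. The interaction estimate becomes the arm difference in (month-3 mean − γx̄) − (baseline mean − γx̄). With complete visits each arm has the same x̄ at both times, so the γ terms cancel. They cancel in the same way from each participant's change in residual, so the robust SE is also unchanged.

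A fit to 500 simulated participants (independence GEE, robust SE, covariate imbalanced by an expected 0.2 SD) confirms this:

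- Two visits, unadjusted: 0.2687 (SE 0.5614). Main effect added: the same to 8 decimals. Covariate-by-month terms: −0.5151 (SE 0.5344).
- Four visits, joint p: 0.226 unadjusted, 0.226 with a main effect, 0.0016 with covariate-by-month terms.

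**4. Size, with and without missing data.** Simulation with 8,000 replicates, n = 500, no true effect, z fixed at 2.5, R = 0.3, and baseline to month-3 correlation 0.7 (assumed). The last column uses five covariates with month terms. Shifts are in SE:

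| Month-3 data | Unadjusted | Main effect | Covariates by month |
|---|---|---|---|
| Complete | 0.748 | 0.748 | −0.007 |
| 20% missing completely at random | 0.633 | 0.632 | −0.002 |
| Dropout rising with the covariate, intervention arm only | 0.276 | 0.222 | −0.013 |

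Rejection rates with complete data were 11.0%, 11.0% and 5.3%. With 20% missing at random, a main effect moved single estimates by 0.016 SE on average (maximum 0.20), and the mean shift was not removed. With covariate-dependent dropout it moved them by 0.106 SE on average (maximum 0.54).

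**5. Nutritional quality.** The invariance does not carry over to a logistic model, but another problem appears. The simulation used a binary item outcome as a simplification, with 500 customers, 20 items per order, two months, customer SD 0.8 and true log odds ratio 0.5, all assumed. Interaction log odds ratios:

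| Covariate | Unadjusted | Conditional, by month | Standardised |
|---|---|---|---|
| Exactly balanced (log odds 1.0 per SD at both months) | 0.380 | 0.445 | 0.380 |
| Imbalanced at z = 2.5 (log odds 0.5 at baseline, 1.0 at month 3) | 0.453 | 0.442 | 0.377 |

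The conditional odds ratio moves without any imbalance and hides most of a real imbalance shift. The standardised contrast returns close to the balanced-data value in both rows.

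**The case against.** The strongest reply is that no primary result depends on this. The analysis is labelled a sensitivity analysis, the primary test keeps its unconditional 5% error, and an unchanged estimate after a main-effect adjustment correctly reflects that change from baseline is immune to time-constant effects. That stands, and it limits the point to covariates related to change.

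Next, if no imbalance is detected, it can be argued that there is nothing to reanalyse. This stands only in part, because significance does not measure whether an imbalance matters. The changes-nothing result also needs several conditions together: a flagged covariate, a main-effect reading, a linear outcome and complete visits. That is correct, and the documents give no complete-visit rate.

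The magnitudes are selected cases. Under randomisation |z| ≥ 2.5 has probability about 1.2% per covariate, and |z| between 1.9 and 1.96 about 0.7%. The candidate count is inferred, and adding health-survey or pre-baseline order data would lower the chance of no flag. These limits stand, but more candidates would repair neither weakness.

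A fixed list could itself miss a large chance imbalance in a covariate left off it, such as race, education or smoking, and nothing in the documents shows that any given covariate predicts change. This is a real trade-off. The non-collapsibility figure also rests on a strong covariate: the conditional log odds ratio moves about 17% at log odds 1.0 per SD, but 4–5% at 0.5 and 1% at 0.25.

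Finally, the plan adds that "We will evaluate sensitivity to missing data by inverse probability of weighted GEE and multiple imputation". Those analyses address missing data and do not test baseline imbalance.

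**Conclusion.** The point holds and is minor. The selection rule is poor in itself: it ignores prognosis and can easily produce an empty adjustment. That chance is at least 66% for 8 candidates and 49% for 14, and about 36% for 20 independent ones.

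The unstated form of entry matters because the simplest reading, main effects only, makes the check empty for the linear outcomes in participants with complete visits. That part is algebra and needs no assumed values. The size of what goes undetected does depend on assumptions: at z = 2.5 it runs from 0.25 SE (conditional error 5.6%) at correlation 0.1 to 0.75 SE (10.5%) at correlation 0.3. These are conditional figures for assumed imbalances and do not describe the trial's overall error rate.

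**What to change.** Delete the p<0.05 criterion and report baseline balance descriptively. Run one adjusted sensitivity analysis per outcome, whatever the balance shows, with a short list fixed in advance on expected relation to change. Covariates already collected would serve, for example age, gender, language, children in household, and enrolment before or after the March 2020 change in pantry procedures.

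- **Continuous outcomes:** keep the GEE and enter the covariates with covariate-by-month terms, so that a difference from the primary analysis reflects the covariates and not a new estimator. A month-3 ANCOVA on the baseline outcome may be reported separately as a precision analysis, noting that it changes the estimator and uses only participants with both values.
- **Nutritional quality:** use the same covariates with month interactions, leave out the baseline outcome while baseline rows are in the response, and compare arms on a standardised (marginal) scale.

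This needs a few sentences in the plan and no new data. If all five covariates were irrelevant, the linear models would lose √(1 + 5/492) = 1.005, or about 0.5% in SE. The standardised comparison takes slightly more work, for example a customer-level bootstrap for its interval. A chance imbalance in an unlisted covariate would show in the descriptive table but would not be adjusted for, so the team should choose the list with that in mind.
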